2.3.3 Analysis method addressing the efficacy estimand for the primary endpoints

The efficacy estimand for % weight change will be assessed using a mixed model for repeated measurements (MMRM). The MMRM will use assessments only from subjects who are taking the randomised treatment until end of trial or at first discontinuing of trial drug (either temporarily or permanently). A pause of less than eight consecutive days is not regarded as discontinuation for this analysis. This means that assessments at week 56 for retrieved drop-outs (type AD) will be discarded. The MMRM will be fitted using % weight change and the same factors and covariates (see [Table 2-4](#)) as for the primary analyses all nested within visit. An unstructured covariance matrix for measurements within the same subject will be employed, assuming that measurements for different subjects are independent.

The efficacy estimand for 5% responders will be assessed using the same MMRM. From the MMRM individually predicted values for % weight change at week 56 will be used to classify each subject as 5% responder or not. This classification will then be analysed using a logistic regression model with treatment and sulphonylurea (yes/no) as the only factors.

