8.3.1 Body weight

The body weight should be measured at all visits without shoes, on an empty bladder and only wearing light clothing. It should be measured on a digital scale to the nearest 0.1 kg or lbs using the same scale throughout the trial. The scale must be calibrated yearly as a minimum.

Body mass index will be calculated by the eCRF from visit 1 data and must be in accordance with inclusion criterion #6. BMI will be calculated as follows:

$BMI = \text{weight (kg)} / \text{height}^2 \text{ (m}^2\text{)}$ or

$BMI = (\text{weight (lb)} / \text{height}^2 \text{ (inch}^2\text{)}) * 703$

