In addition, an efficacy estimand (*de jure*) is quantifying the average effect of liraglutide 3.0 mg relative to placebo 56 weeks after randomisation, as adjunct to reduced caloric diet and increased physical activity, if all randomised subjects had adhered to the assigned treatment regimen for the entire planned duration of the trial.

Taxonomy of week 56 assessments being available or missing

A given assessment at week 56 may be available or missing. [Table 2-1](#) describes the taxonomy for this. Note that this is done per assessment not per subject, as subjects may belong to different types for different assessments (a subject may have “available on treatment (AT)” for weight but “missing on treatment (MT)” for waist circumference).

Table 2–1 Taxonomy of week 56 assessments being available or missing

Assessment at week 56	On randomised treatment at week 56	Type description	Type Abbreviation
Available	Yes	Available on randomised treatment: Subjects who did not discontinue randomised treatment prematurely. Include those that stop and restart trial product.	AT
	No	Available drop-outs: Subjects who discontinued randomised treatment prematurely but returned to have an assessment at week 56; so-called retrieved drop-outs.	AD
Missing	Yes	Missing on randomised treatment: Subjects who did not discontinue randomised treatment prematurely. Include those that stop and restart trial product.	MT
	No	Missing drop-outs: Subjects who discontinued randomised treatment prematurely and did not return to have an assessment at week 56; so-called non-retrieved drop-outs.	MD

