2.1 Sample size calculation

The sample size calculation is based on the analysis approach addressing the primary estimand for the primary endpoints change in body weight (%) from baseline to week 56 (% weight change) and proportion of subjects losing $\geq 5\%$ of baseline body weight at week 56 (5% responders).

The two primary endpoints and all confirmatory secondary endpoints will be tested in a hierarchical order.

The study design is a 1:1 randomisation, stratified by sulphonylurea (yes/no) with 400 subjects in total (200 subjects in each arm). The sample size calculation does not take stratification into account. Please see [Table 2–2](#) for general specifications on sample size and power calculation.

Table 2–2 General specifications for sample size and power calculation

Endpoint	Statistical test	Minimum required power (%)
% weight change	Two-group Satterthwaite unpooled t test on the mean difference with $\alpha=0.05$ assuming unequal variances	90.0 (marginal)
5% responders	Pearson chi-square test for two independent proportions with $\alpha=0.05$	90.0 (marginal)

α : two-sided significance level

In the following paragraphs treatment differences and standard deviations (SD) are given without units.

Body weight measurements from returning discontinuing subjects will be used in the primary analysis. But for the sample size calculations, it is assumed that all subjects who discontinue will not return at week 56 and assume that they have a % weight change like placebo subjects who completed the trial. It is expected that % weight change for liraglutide 3.0 mg subjects who discontinue might be somewhere in between completing placebo subjects and completing liraglutide 3.0 mg subjects. The assumption is thus expected to lead to a conservative effect estimate. A 30% discontinuation is assumed based on findings in trial NN8022-1922.

Based on findings from NN8022-1922, a difference in % weight change between liraglutide 3.0 mg and placebo of -4 (-6% vs. -2% , $SD=6$) is assumed among completing subjects. Adjusting for 30% discontinuation and using a mixture distribution, a difference of -2.8 is expected in the primary analysis. A sample size of 400 subjects (200 in each arm), gives a marginal power of 99.5%.

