2.3.2 Handling of missing values for the effectiveness estimand

2.3.2.1 Handling of missing values at baseline

If an assessment has been made both at screening and randomisation, the value from the randomisation visit will be used as the baseline value. If the value measured at the randomisation visit is missing and the assessment was made at screening, the screening value will be used as the baseline value.

2.3.2.2 Handling of missing values at week 56

Missing values at week 56 will be imputed and the relevant endpoints will be derived from the imputed values. Several approaches for imputation of missing values at week 56 will be applied. First, a description of the primary imputation approach used to address the effectiveness estimand for the primary endpoints is given. This is followed by a description of a number of sensitivity analyses.

Primary approach for handling of missing values

The primary approach for multiple imputations of missing values of body weight at week 56 (type MT+MD) for both the liraglutide 3.0 mg and placebo group is by sampling among all available assessments at week 56 in the placebo group (type AT+AD). This approach is also known as jump to reference and makes the assumption that subjects instantly after discontinuation lose any effect of randomised treatment beyond what can be expected from placebo treatment as adjunct to diet and exercise¹. Body weight measurements at visits between baseline and week 56 are not used for this imputation approach. The multiple imputation approach is done in three steps.

- **Imputation:** Step 1 defines an imputation model based on placebo subjects, which is used to impute missing body weight values at week 56 in both arms. This will be done 100 times

and results in 100 complete data sets. A more detailed explanation of this step is given below.

- **Analysis:** Step 2 analyses each of the 100 complete data sets, using the statistical model defined in Sections [2.3.1.1](#) and [2.3.1.2](#), and saves the 100 estimation results.
- **Pooling:** Step 3 integrates the 100 estimation results into a final result using Rubin's formula.

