2.4 Secondary endpoints

2.4.1 Confirmatory secondary endpoints

Confirmatory secondary endpoints are listed in Section **4.2.2.1** in the protocol.

All confirmatory secondary endpoints are planned to be assessed at week 56 and will be analysed using the same MI approach as used for the primary endpoints and to address the effectiveness estimand. The statistical models for continuous endpoints will be ANCOVA with factors and covariates listed in [Table 2-4](#) with baseline body weight replaced by baseline measurement of endpoint to be analysed. The statistical model for 10% responders will be analysed using logistic regression in the same way as for 5% responders.

Sensitivity analyses will be carried out for all confirmatory secondary endpoints. See [Table 2-6](#) for details on planned analysis methods, multiple imputation approach and sensitivity analyses.

The efficacy estimand will also be assessed for confirmatory secondary endpoints using MMRM as described for the primary endpoints.

2.4.2 Description of the testing procedure to address the effectiveness estimand for primary and confirmatory secondary endpoints

The tests of superiority of liraglutide 3.0 mg to placebo for each of the endpoints are tested in a hierarchical manner in the order in which the endpoints are presented. The two primary endpoints are included in the statistical testing hierarchy below, even though the primary objective will only be met if superiority of liraglutide 3.0 mg vs. placebo is demonstrated for each of the primary endpoints. The test hierarchy is given in [Table 2-6](#). The first endpoints to be tested are all assessing aspects of weight loss (e.g., relative change in body weight, achieving a certain magnitude of weight loss, and change in waist circumference); these endpoints are followed by endpoints assessing change in weight-related comorbidities and/or consequences of excess body weight and 'feeling and function' indicators.

Table 2–6 Hierarchical order and type of statistical model to address the effectiveness estimand for primary and confirmatory secondary endpoints

Test order	Endpoint	Endpoint type	Statistical model	MI approach	Sensitivity analyses #
Primary endpoint					
1	Change in body weight (%) from baseline to week 56	Continuous	ANCOVA	Jump to reference	McEvoy wANCOVA Sacks Tipping point Unadjusted ANCOVA

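### Efficacy-estimand 5% responders are obtained by thresholding MMRM predictions and analysed once as if observed, so the rates and odds ratio can be wrong, the standard error is too small, and the type of prediction is not stated

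*SAP*

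**What the plan says.** SAP section 2 (Definition of Estimands) defines the additional, efficacy estimand as the effect "if all randomised subjects had adhered to the assigned treatment regimen for the entire planned duration of the trial". For % weight change, SAP 2.3.3 fits an MMRM with unstructured covariance to data up to first discontinuation of trial drug, so that "assessments at week 56 for retrieved drop-outs (type AD) will be discarded".

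For 5% responders the same MMRM supplies the classification: "individually predicted values for % weight change at week 56 will be used to classify each subject as 5% responder or not". The next sentence is: "This classification will then be analysed using a logistic regression model with treatment and sulphonylurea (yes/no) as the only factors". Protocol 17.3.3 gives the same rule. Neither document adds a residual draw, repeated imputation, pooling or any other variance correction. Neither says whether the prediction is conditional on the subject's own on-treatment weights or is the fixed-effects mean, or whether observed week 56 values are kept.

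For the effectiveness estimand, SAP 2.3.2.2 does use multiple imputation: "Step 3 integrates the 100 estimation results into a final result using" Rubin's formula. SAP 2.4.1 then states: "The efficacy estimand will also be assessed for confirmatory secondary endpoints using MMRM as described for the primary endpoints". Those endpoints include 10% responders.

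**The concern.** A model prediction for a subject with no on-treatment week 56 value is an expected value. Predictions vary less between subjects than real outcomes do, so the share of predictions at or below −5% does not estimate the share of subjects who would have lost at least 5%. This holds even with a correct MMRM and data missing at random. Entering predicted classes in one logistic regression as if they were data also ignores prediction error, so the standard error is too small.

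At stake are the responder rates, odds ratio and confidence interval reported under the efficacy estimand for a co-primary endpoint, and by extension for 10% responders. Because the type of prediction is left open, two programmers following the text could report very different odds ratios.

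**Working it through.** **Inputs from SAP 2.1.** Means −6 (liraglutide) and −2 (placebo), SD 6, 30% discontinuation, 200 per arm. The responder cut of −5% is in SAP section 2. **Assumed, because the documents give neither:** ρ, the correlation between on-treatment history and the week 56 value, and the drop-out mechanism. Drop-out is set at 30% in each arm.

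**Step 1: reproduce the plan's figures.** Completer responder rates are Φ((−5+6)/6) = Φ(0.167) = 56.6% and Φ((−5+2)/6) = Φ(−0.5) = 30.9% (plan: 57% and 31%). The liraglutide mixture rate is 0.7×56.6 + 0.3×30.9 = 48.9% (plan: 49%). Power for 49% vs 31% comes to 95.9% (plan: 95.7%). The inputs are read correctly.

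**Step 2: target.** Under full adherence the odds ratio is (0.566/0.434)/(0.309/0.691) = 2.92.

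**Step 3: conditional prediction, random drop-out.** A drop-out's prediction has SD 6ρ instead of 6. At ρ = 0.7 this is 4.2, so predicted responder rates in drop-outs are Φ(1/4.2) = 59% and Φ(−3/4.2) = 24%, against true rates of 57% and 31%. Overall: 0.7×0.566 + 0.3×0.594 = 57.5% and 0.7×0.309 + 0.3×0.238 = 28.7%, an odds ratio of 3.35.

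**Step 4: other mechanisms.** Drop-out log-odds were taken as c + b·z, with z the standardised on-treatment history (high = poor response), c set to give 30%, and b = 1 or 2. Large-sample odds ratios used 4 million subjects per arm. Coverage is from simulated trials of 200 per arm: 1,000 per scenario in the first three rows, and 1,500 without covariates in the last two. The last two rows shift the means so that completers, rather than all subjects, average −6 and −2.

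| Drop-out | Thresholded OR at ρ 0.9 / 0.7 / 0.5 | True OR | Coverage of 95% CI |
|---|---|---|---|
| Random | 3.03 / 3.35 / 3.95 | 2.92 | 94 / 86 / 64% |
| b = 1 | 2.97 / 3.15 / 3.47 | 2.92 | 94 / 87 / 80% |
| b = 2 | 2.88 / 2.90 / 3.05 | 2.92 | 93 / 92 / 87% |
| b = 1, completer means | 3.01 / 3.10 / 3.30 | 2.98 / 2.96 / 2.95 | 95 / 92 / 87% |
| b = 2, completer means | 2.96 / 2.84 / 2.83 | 3.02 / 2.99 / 2.96 | 95 / 93 / 92% |

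A nearly correct odds ratio can hide wrong rates. At ρ = 0.5 and b = 2 the odds ratio is 3.05, but the rates are 52.0% and 26.2% against 56.6% and 30.9%. At ρ = 0.7 and b = 1 the drop-outs are under-classified in both arms: 35% against a true 40% on liraglutide, and 8% against 17% on placebo.

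**Step 5: standard error.** Mean model SE against actual SD of the log odds ratio (first three rows): 0.211 vs 0.220–0.231 at ρ = 0.9, 0.213–0.214 vs 0.234–0.256 at 0.7, and 0.216–0.217 vs 0.276–0.285 at 0.5. The shortfalls are about 4–9%, 9–17% and 21–24%. With no treatment effect (both means −5, random drop-out), where the odds ratio is unbiased, a nominal 5% test rejects in 7%, 9.5% and 15% of trials.

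**Step 6: full visit structure.** A second simulation fitted the unstructured model across visits, with random-walk or constant correlation and uniform or early ignorable drop-out (400 trials per scenario). Thresholding gave odds ratios of 3.11 to 4.35, SE 11–30% below the actual SD, and coverage of 54% to 92%.

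**Step 7: marginal prediction.** With fixed effects only, the prediction SD is 6√R², where R² is the share of variance explained by the covariates (assumed). At R² = 0.10 this is 1.90, so the rates are Φ(1/1.90) = 70% and Φ(−3/1.90) = 6%. For R² = 0.05 / 0.10 / 0.20 / 0.30 the odds ratio is 264 / 39 / 12 / 7.4 if every subject is so classified, and 6.0 / 5.1 / 4.2 / 3.8 if only drop-outs are.

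**Step 8: multiple imputation instead.** With residual and parameter draws and Rubin pooling, the odds ratio was 2.91–2.98 and coverage 94.5–97.7% in 13 scenarios of the Step 4 type (not completer-anchored), and 2.92–2.94 with 94–97% in the Step 6 setting.

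**10% responders.** The true odds ratio is 3.37. Thresholding gives 3.52 / 3.79 / 3.69 (random), 3.35 / 3.31 / 3.19 (b = 1) and 3.31 / 3.18 / 3.09 (b = 2).

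**The case against.** The strongest reply is that little depends on this analysis. The hierarchy tests only the effectiveness estimand, which already has multiple imputation, Rubin pooling and several sensitivity analyses. At the planned effect every simulated trial with conditional prediction was still significant. That stands, and it limits the seriousness of the point.

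Second, the size rests on assumptions. Protocol 8.3.1 says "The body weight should be measured at all visits", so ρ should be high for late drop-outs, and at ρ = 0.9 the conditional error is negligible. In SAP 2.1 the −6/−2 difference "is assumed among completing subjects". With that anchor, outcome-related drop-out and ρ of at least 0.7, the odds ratio is off by about 5% or less and coverage is 92–95%; at ρ = 0.9 and b = 2 the SE and actual SD were equal in one run (0.229 each). The 64% figure needs random drop-out and ρ = 0.5 for every drop-out. All of this stands as to size. It does not make the rule valid.

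Third, a prediction described as individual, from a model with within-subject covariance, is more naturally conditional, so the very large marginal odds ratios belong to the less likely reading. That is fair, but the text does not exclude it.

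Finally, SAP 2.4.1 does not spell out a 10% classification. That 10% responders inherit the method is a reasonable inference, not an explicit statement.

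**Conclusion.** The concern holds: the rule is wrong as written, not merely short of detail. Followed exactly, it does not estimate the on-treatment responder rate, and its confidence interval ignores prediction error.

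Under the conditional reading the damage runs from negligible (high ρ, late drop-out) to material (many early drop-outs). The direction of the odds-ratio error depends on the arm means, ρ and who drops out. Under the marginal reading the error is large. The share of predicted subjects may exceed 30%, because SAP 2.3.3 stops at the first discontinuation even if temporary, while Table 2-1 counts subjects who restart as on treatment.

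The primary effectiveness analysis, the test hierarchy, its type I error and the continuous MMRM result are not affected. The mechanism is certain; the size depends on ρ and the drop-out pattern, which the documents do not give. It should be fixed.

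**What to change.** Replace the last two sentences of SAP 2.3.3 with text to this effect:

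> Week 56 % weight change that is missing, or was measured after first discontinuation, will be imputed 100 times under a missing-at-random model matching the MMRM (same factors and covariates by visit, unstructured covariance). Imputation will condition on the subject's own on-treatment data and include residual variance and parameter uncertainty. Observed on-treatment week 56 values will be kept. Responder status will be derived in each data set, analysed with the logistic model on treatment and sulphonylurea, and pooled by Rubin's formula. 10% responders will be handled in the same way.

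The logistic model is unchanged. Because Protocol 17.3.3 carries the same rule, the change should be listed in SAP 3.1. If thresholding is kept, the SAP should at least state that the prediction is conditional on the subject's own on-treatment data and that the interval ignores prediction error.

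The cost is wording and modest programming, with no new data. Expect a wider, slightly conservative interval and possibly a smaller odds ratio. The 13-scenario check of this fix used a single last on-treatment value as a stand-in for the full MMRM, and the visit-level check assumed monotone drop-out. Handling of intermittent gaps was not tested and should be specified in the program.

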2.3.4 Subgroup analyses for primary endpoints

For the effectiveness estimand, subgroup analyses will be done for the factors listed and categorised as in [Table 2-4](#). For baseline weight, categories based on quartiles will be used. The subgroup analyses will be done separately for each of these by including interaction term(s) with randomised treatment arm in the respective models (ANCOVA or logistic regression).

2.3.5 Exploratory analysis of change in body weight

Two exploratory analyses of change in body weight (%) taking into account the change in total daily insulin use from baseline (week 0) to week 56 will be conducted. Change in total daily insulin dose (U) is calculated by subtracting the total daily basal insulin dose (U) at baseline from the average total daily insulin dose (U) from baseline or week 44 to week 56. The change in total daily insulin dose will also be grouped into 4 groups based on the median for subjects with a change < 0 and the median for subjects with a change ≥ 0 . Change in body weight will be analysed using a analysis of covariance (ANCOVA) including treatment, gender, BMI group and grouped change in total daily insulin as factors and baseline body weight in kg as a covariate and an interaction between change in total daily insulin dose and the grouped change in total daily insulin dose.

Figure 2–1 Illustration of imputation approaches

[figure not shown]

Table 2–5 Overview of handling of missing values

Approach	Description	Assumptions
Jump to reference (multiple imputation)	Liraglutide and placebo MT+MD imputed from placebo AT+AD (i.e., all available placebo assessments at week 56)	- Liraglutide MD lose any treatment effect instantly after drop-out - Placebo AT and placebo AD are assumed to have same weight loss
McEvoy (multiple imputation)	Separately for the two randomised treatment arms: MD imputed from AD by matching on time (month) of drop-out MT imputed from AT	- AD is representative of the MD for each randomised treatment arm - AT is representative of the MT for each randomised treatment arm
Weighted ANCOVA (wANCOVA)	No imputation. Separately for the two randomised treatment arms: AD subjects are up-weighted relative to their proportion of AD+MD and timing of drop-out AT subjects are up-weighted relative to their proportion of AT+MT	- AD is representative of the MD for each randomised treatment arm - AT is representative of the MT for each randomised treatment arm
Sacks (single imputation)	Liraglutide MD imputed by minimum of LAO+0.3 kg and baseline value for each month from drop-out to week 56 and either a) Placebo MD imputed by minimum of LAO+0.3 kg and baseline value for each month from drop-out to week 56 or b) MT (both randomised treatment arms) and placebo MD are imputed by LAO	a) Liraglutide and placebo MD lose any treatment effect linearly after drop-out. b) Only liraglutide MD lose any treatment effect linearly after drop-out. No change in treatment effect since LAO for others.
Tipping point (single imputation)	Liraglutide MD imputed by minimum of LAO+X kg (X in steps of 0.1) and baseline value for each month from drop-out to week 56. MT (both randomised treatment arms) and placebo MD are imputed by LAO	Only liraglutide MD lose any treatment effect linearly after drop-out. No change in treatment effect since LAO for others

AT available on randomised treatment, MT missing on randomised treatment, AD available drop-out, MD missing drop-out, LAO last available observation, LAO-OT last available observation on randomised treatment.

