to account for the subjects not returning for assessments at week 56⁴⁴. Similarly, AT subjects are up-weighted relative to their proportion of all drug continuing subjects (AT+MT). The up-weighting is done by randomised treatment arm and the timing of LAO-OT. Subjects who are missing the weight measurement at week 56 (MD+MT) are assigned a weight of 0 (zero).

- A single imputation approach as done by Sacks³. Missing weight measurement at week 56 for subjects who drop-out (type MD) are imputed using a weight regain rate of 0.3 kg/month after last available observation (LAO) of body weight. Change from baseline is truncated whenever the extrapolation would lead to a positive weight gain relative to baseline. LAO does not need to be the same as LAO-OT as subjects are allowed to come to scheduled visits after discontinuing randomised treatment. When a subject's LAO represents a gain in weight relative to baseline, no additional gain will be imputed, and the unfavourable gain is carried forward to week 56. Missing weight measurement at week 56 for subjects on treatment (type MT) will be imputed using the LAO. The weight regain imputation will be done for both randomised treatment arms. Additionally, a version where only the liraglutide 3.0 mg arm uses the regain rate while the placebo arm uses LAO (corresponding to a weight regain rate of 0 kg/month) will be performed.
- Tipping point analysis. In a similar manner as above for a range of weight regain rates (starting from 0.1 kg/month and in intervals of 0.1 kg/month) for MD in liraglutide 3.0 mg arm will be used to define a tipping point in which superiority of liraglutide 3.0 mg disappears. In this analysis, the placebo arm will be imputed by LAO.

[Figure 2-1](#) and [Table 2-5](#) give an overview of the handling of missing values at week 56 assessments.

Additional sensitivity analyses

Additional analyses will investigate how sensitive the primary statistical models (for primary endpoints) are to the choice of factors and covariates in the model as follows. A model resembling the primary analysis models using the same imputation method (jump to reference) adjusting only for baseline body weight and randomised treatment arm. The imputation model (step 1) will be same as for the primary approach.

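### SAP Table 2-5 resets missing liraglutide drop-outs who had gained weight to baseline, while the SAP text carries the gain forward

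*SAP*

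**What the plan says.** SAP 2.3.2.2 sets out a single-imputation analysis for missing drop-outs (MD): weight regain of 0.3 kg/month added to the last available observation (LAO), counted from the LAO. Two rules limit it.

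- LAO at or below baseline: "Change from baseline is truncated whenever the extrapolation would lead to a positive weight gain relative to baseline".
- LAO already above baseline: where it represents "a gain in weight relative to baseline, no additional gain will be imputed, and the unfavourable gain is carried forward to week 56".

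Version a applies the regain to both arms. Version b applies it to liraglutide only and leaves placebo at LAO. The tipping-point analysis then runs "In a similar manner as above for a range of weight regain rates", with placebo at LAO, and the scan "will be used to define a tipping point in which superiority of liraglutide 3.0 mg disappears".

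SAP Table 2-5 restates these analyses differently. Its regain row reads "Liraglutide MD imputed by minimum of LAO+0.3 kg and baseline value for each month from drop-out to week 56" and its tipping-point row "Liraglutide MD imputed by minimum of LAO+X kg (X in steps of 0.1) and baseline value". For version b and the tipping point, "MT (both randomised treatment arms) and placebo MD are imputed by LAO". The stated assumption is "Only liraglutide MD lose any treatment effect linearly after drop-out". No row makes an exception for a subject who is already above baseline.

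Protocol 17.3.2.2 and protocol Table 17-5 carry the same pair of rules.

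**The concern.** The minimum of (LAO plus regain) and baseline is baseline whenever the LAO exceeds baseline. The table therefore improves a liraglutide subject who had gained weight, where the text keeps the gain. It also conflicts with the table's own assumption that these subjects lose effect after dropping out.

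In version b and the tipping-point analysis the reset applies to liraglutide only. Both are meant to stress the liraglutide result, so a rule that helps that arm works against their purpose. The same subject has two pre-specified week 56 values, and a scan for % weight change that is close to tipping could tip under one and not under the other.

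**Working it through.** **1. The plan's figure.** From SAP 2.1: completers -6 vs -2, SD 6, 30% discontinuation, 200 per arm. The liraglutide mean is 0.7 × (-6) + 0.3 × (-2) = -4.8, so the difference from placebo is -2.8. The mixture SD is √(36 + 0.7 × 0.3 × 4²) = 6.27. A Satterthwaite t test then has 99.5% power, as stated.

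**2. Both rules on single subjects** (baseline 100 kg, 6 months from LAO to week 56, no gap between drop-out and LAO; rates 0.1, 0.3 and 1.0 kg/month).

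| LAO | Text, liraglutide MD | Table, liraglutide MD | Placebo MD (version b, tipping point) |
|---|---|---|---|
| 95 kg | 95.6, 96.8, 100 | 95.6, 96.8, 100 | 95 |
| 103 kg | 103 at every rate | 100 at every rate | 103 |

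The cap works identically under both rules. Only subjects above baseline differ, and the rate does not matter for them.

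**3. Size of the gainer effect.** With m the MD share and LAO % change taken as normal with mean μ and SD s:

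shift towards liraglutide = m × E[max(0, LAO)] = m × [s φ(μ/s) + μ Φ(μ/s)]

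The documents give none of m, μ and s. Assumed ranges: m 5% to 30%, μ -6% to -1%, s 3 to 6.

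- Mid case, μ -4, s 4 (16% gainers): the bracket is 0.333. Shift 0.333 × 0.15 = 0.05 to 0.333 × 0.30 = 0.10.
- Upper corner, μ -1, s 6: 1.927 × 0.30 = 0.58.
- Lower end, μ -6, s 3: 0.025 × 0.30 = 0.008, and less at smaller m.

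**4. Effect on the scan at its capped limit** (regain so large that every MD not already above baseline sits at baseline). Discontinuers who return are assumed placebo-like, at -2%.

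- 30% MD, placebo LAO -2%: the table rule gives 0.7 × (-6) + 0.3 × 0 - (-2) = -2.20, with SE √((32.76 + 36)/200) = 0.586. The mid-case text rule gives -2.10.
- 30% MD, placebo LAO -4%: the placebo mean is 0.7 × (-2) + 0.3 × (-4) = -2.6, so the table rule gives -1.60 and the text rule -1.50.

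Both rules were then applied to the same simulated trials (20,000 per setting for the mid case, 40,000 for the corner). Share of trials in which the text rule tips and the table rule does not:

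| Setting | Placebo LAO -2% | Placebo LAO -4% |
|---|---|---|
| Mid case, 15% MD | 0.3% | 0.9% |
| Mid case, 30% MD | 1.5% | 6.1% |
| Corner: 30% MD, μ -1, s 6 | 22% | 41% |

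**5. The second difference in the same rows.** The table counts months from drop-out and the text from LAO. A subject weighed after stopping drug gets more months of regain under the table. In version b and the tipping-point analysis that extra regain falls on liraglutide only. At 0.3 kg/month (baseline 100 kg, 1 to 13 months left, assumed), table minus text per liraglutide MD, negative favouring liraglutide:

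- μ -4, s 4: -0.33 points with no gap between stopping and LAO, -0.04 at 1.5 months, +0.06 at 2 months.
- μ -4, s 3: +0.09 at 1 month.
- μ -2, s 6: -1.24 at 2 months.

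The sign therefore depends on unknown inputs. At the capped limit the month count drops out and only the gainer effect remains.

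**6. Version a.** The table resets both arms. With equal LAO distributions the gainer effect cancels. With liraglutide -4, placebo -2 and SD 6 at 30% MD, it is (1.525 - 0.907) × 0.30 = 0.19 points against liraglutide.

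**7. Responders.** A subject at or above baseline is a non-responder at both 5% and 10%, so the gainer rule changes nothing there.

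**The case against.** The strongest defence is that the detailed rule is already written. SAP 2.3.2.2 deals with gainers explicitly and presents Table 2-5 as an overview, so a programmer who follows the text gets the intended value. This stands in part: harm needs the shorthand to be preferred to the full rule. But neither document says which governs. The sensitivity-analysis column of Table 2-6 sends the reader to Table 2-5, and SAP section 3 does not mention the conflict. Figure 2-1, cited alongside the table, is not shown in the copy reviewed and could not be checked.

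Two further objections stand in full. A reader might infer that programming the table always tilts version b and the tipping-point scan towards liraglutide; step 5 shows that the month count can cancel or reverse this at finite rates. A reader might also take 22% to 41% as the typical chance of a changed conclusion. Those figures need every discontinuer to be lost and liraglutide drop-outs to have lost less weight than placebo drop-outs. SAP 2.1 expects liraglutide discontinuers to fall between the two completer groups, and says that weights from those who return will be used.

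The cap at baseline is not an error: the text discloses it.

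**Conclusion.** The contradiction is certain and rests on no assumption: text and table give different week 56 weights for any MD whose LAO is above baseline. Taken alone, the table's gainer rule favours liraglutide in the tipping-point analysis and in version b, by about 0.05 to 0.10 points in the mid case and 0.00 to 0.58 over the assumed inputs. At the capped limit it turns a tip into no tip in about 0.3% to 6% of trials in the mid case. The sizes rest on the assumed LAO distribution, MD share and placebo LAO mean.

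The net direction of programming the whole row is secure only at the capped limit; in version a it depends on the LAO values. The documents do not support reading this as a threat to the main conclusion. The primary jump-to-reference analysis, the weighted ANCOVA and the imputation from retrieved drop-outs do not use this rule, and the 5% and 10% responder results do not change with it. Severity is minor.

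**What to change.** Rewrite the 0.3 kg/month regain row (versions a and b) and the tipping-point row of SAP Table 2-5 so that they match SAP 2.3.2.2:

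- MD with LAO at or below baseline: the smaller of baseline and LAO + rate × months from LAO to week 56.
- MD with LAO above baseline: LAO, at every rate.
- Placebo MD in version b and in the tipping-point analysis: LAO, as now.

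This settles both the gainer rule and the starting point for counting months. Protocol Table 17-5 has the same wording, so a line in SAP section 3 can record the correction. The cost is table wording only: no new data, no new analysis and no change to the primary test.
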